### **13.4 Language**

All written information and other material to be used by patients and investigative staff must use vocabulary and language that are clearly understood.

### **13.5 Publication Policy**

To coordinate the dissemination of data from this trial, a publication committee may be formed consisting of both Principal Investigators and appropriate Lilly staff. The committee is expected to solicit input and assistance from other Investigators and Lilly staff as

appropriate. Membership on the committee (both for Investigators and Lilly staff) does not guarantee authorship. The criteria described below should be met for every publication.

Authorship of any publications resulting from this trial will be determined on the basis of the Uniform Requirement for Manuscripts Submitted to Biomedical Journals (International Committee of Medical Journal Editors, 2016), which states:

- Authorship credit should be based on (1) substantial contributions to conception and design, acquisition of data, or analysis and interpretation of data; (2) drafting the article or revising it critically for important intellectual content; (3) final approval of the version to be published. Authors should meet conditions 1, 2, and 3.
- When a large, multi-center group has conducted the work, the group should identify the individuals who accept direct responsibility for the manuscript. These individuals should fully meet the criteria for authorship defined above.
- Acquisition of funding, collection of data, or general supervision of the research group, alone, does not justify authorship.
- All persons designated as authors should qualify for authorship, and all those who qualify should be listed.
- Each author should have participated sufficiently in the work to take public responsibility for appropriate portions of the content.

All publications (eg, manuscripts, abstracts, oral/slide presentations, book chapters) based on this trial must be submitted to Lilly for corporate review. The Clinical Trial Agreement between the institution, principal Investigator, and Lilly will detail the procedures for and timing of Lilly review of publications.

## **15.0 APPENDICES**

**Appendix A – Schedule of Assessments**

| Assessments
(Both trial Arm 1 and Arm 2 will follow the same schedule of assessments unless otherwise noted) | Screening                       | Treatment Cycles
(1 Cycle = 4 Weeks) |        |         |        |                      |        | End of Treatment               | Extended Safety Observation Period    | Long-term Survival Follow-up            |
|---|---------------------------------|---|--------|---------|--------|----------------------|--------|--------------------------------|---------------------------------------|---|
|   |                                 | Cycles 1, 3, 5, etc.                    |        | Cycle 2 |        | Cycles 4, 6, 8, etc. |        |                                |                                       |   |
| Relative day  | Within 21 days of randomization | Day 1                                   | Day 15 | Day 1   | Day 15 | Day 1                | Day 15 | 28 days ±7 days from last dose | 60 and 90 days ±7 days from last dose | Every 8, 12, or 16 weeks a,b |
| GENERAL AND SAFETY AWARENESS   |                                 |   |        |         |        |                      |        |                                |                                       |   |
| Informed consent  | X                               |   |        |         |        |                      |        |                                |                                       |   |
| Medical/cancer history and demographics   | X                               |   |        |         |        |                      |        |                                |                                       |   |
| Physical examination (include Ht [screening only] & Wt)   | X                               | X                                       |        |         |        |                      |        | X                              |                                       |   |
| Vital signs   | X                               | X                                       |        |         |        |                      |        | X                              |                                       |   |
| ECOG performance status   | X                               | X                                       |        |         |        |                      |        | X                              |                                       |   |
| 12-Lead ECG   | X                               | X                                       |        |         |        |                      |        | X                              |                                       |   |
| Concomitant medication  | X                               | ← X →                                   |        |         |        |                      |        |                                |                                       |   |
| Adverse event   | Post Randomization              | ← X →                                   |        |         |        |                      |        |                                |                                       |   |
| LABORATORY ASSESSMENTS   |                                 |   |        |         |        |                      |        |                                |                                       |   |
| Hematology, chemistry   | X                               | X                                       | X      | X       | X      | X                    | X      | X                              |                                       |   |
| aPTT and INR or PT  | X                               | X                                       | X      | X       | X      | X                    | X      | X                              |                                       |   |
| Thyroid function test (TSH, free T3, and free T4)   | X                               | X                                       |        |         |        |                      |        | X                              |                                       |   |
| Pregnancy test  | X                               | X                                       |        |         |        |                      |        | X                              |                                       |   |
| Urinalysis  | X                               | X                                       |        |         |        |                      |        | X                              |                                       |   |
| PD-L1 status  | X c                  |   |        |         |        |                      |        |                                |                                       |   |
| Tumor sample for biomarker research d  |                                 | Submitted once during study treatment   |        |         |        |                      |        |                                |                                       |   |
| PK, ADA, AND BIOMARKERS  |                                 |   |        |         |        |                      |        |                                |                                       |   |
| ADA (required Arms 1 and 2) e  |                                 | X                                       |        | X       |        | X                    |        | X                              | X                                     |   |
| PK (required Arm 1 and crossover) e  |                                 | X                                       |        | X       |        | X                    |        | X                              | X                                     |   |
| Biomarkers (required Arms 1 and 2) f   |                                 | X                                       |        | X       |        |                      |        | X                              |                                       |   |

| Assessments
(Both trial Arm 1 and Arm 2 will follow the same schedule of assessments unless otherwise noted) | Screening                       | Treatment Cycles
(1 Cycle = 4 Weeks)  |        |         |        |                      |        | End of Treatment               | Extended Safety Observation Period    | Long-term Survival Follow-up            |
|---|---------------------------------|--|--------|---------|--------|----------------------|--------|--------------------------------|---------------------------------------|---|
|   |                                 | Cycles 1, 3, 5, etc.   |        | Cycle 2 |        | Cycles 4, 6, 8, etc. |        |                                |                                       |   |
| Relative day  | Within 21 days of randomization | Day 1  | Day 15 | Day 1   | Day 15 | Day 1                | Day 15 | 28 days ±7 days from last dose | 60 and 90 days ±7 days from last dose | Every 8, 12, or 16 weeks a,b |
| TRIAL TREATMENT  |                                 |  |        |         |        |                      |        |                                |                                       |   |
| Arm 1 AM0010
Arm 1 & Arm 2 nivolumab   |                                 | QD (Not cycle dependent for either schedule of nivolumab)
Administered Q2W or Q4W; Each cycle = 4 weeks   |        |         |        |                      |        |                                |                                       |   |
| TUMOR AND SURVIVAL ASSESSMENTS   |                                 |  |        |         |        |                      |        |                                |                                       |   |
| Tumor assessment b   | Within 30 days of Randomization | Every 8 weeks (±7 days) during study treatment and during the first year from discontinuation of the study treatment every 12 weeks (±7 days) during the second year every 16 weeks (±7 days) thereafter |        |         |        |                      |        |                                |                                       |   |
| Survival a and treatment status  |                                 |  |        |         |        |                      |        |                                |                                       | X                                       |

Abbreviations: ADA = anti-drug antibody; aPTT = activated partial thromboplastin; ECG = electrocardiogram; Ht = height; INR = International Normalized Ratio; PD-L1 = programmed death ligand-1; PK = pharmacokinetics; PT = Prothrombin time; Q2W = every 2 weeks; Q4W = every 4 weeks; QD = everyday; TSH = thyroid stimulating hormone; Wt = weight.

- a All randomized patients will be followed for survival every 8 weeks (±7 days) during the first year from the 90-day follow-up visit, every 12 weeks (±7 days) during the second year, and every 16 weeks (±7 days) thereafter. The survival follow-up will be conducted until death or the study completion, whichever is first, whether or not trial drug was administered.
- b Tumor assessment will be performed for all randomized patients. Tumor assessment will be repeated until disease progression, death, or receipt of new anti-cancer therapy, or until study completion, whichever is first, whether or not study treatment was administered. When progressive disease is noted on the scan for an Arm 2 patient, no more than 21 days should pass before the patient can be considered for crossover to Arm 1.
- c A fresh tissue biopsy is only required if no archival tissue is available within 60 days of informed consent or unless approved by the Medical Monitor.
- d Mandatory tumor tissue sample for biomarker research should be submitted once the patient is enrolled (preferably from the same block used for PD-L1 testing).
- e ADA and PK samples will be collected on Day 1 of Cycles 1, 2, 3, 4, every fourth cycle thereafter, and at end-of-treatment visit, and at the follow-up visits 60 and 90 days after the last dose of study treatment.
- f Biomarker samples will be collected on Day 1 of Cycles 1, 2, 3, 5, 7, 9, 11, etc. and end-of-treatment visits. Specific biomarker blood collection tubes may vary by time point. See the Lab Manual for details.

**Appendix B – Continued-Access Period Schedule of Assessments**

|   |                  | Study Period              | Continued Access Treatment Cycles
(1 Cycle = 4 weeks) | Continued Access End of Treatment | Continued-Access Extended Safety Observation Period |
|---|------------------|----------------------------------|--|--|--|
|   |                  |                                  | Cycle X-Y  |  |  |
|   |                  | Relative day                     | Day 1  | 28 days ±7 days from last dose           | 60 and 90 days ±7 days from last dose                      |
| Procedure Category                      | Protocol Section | Procedure                        |  |  |  |
| Study Treatment (AM0010)                | 6.0              | Self –Administration QD SC       | X  |  |  |
| Adverse Events Collection/CTCAE Grading | 9.0              | Toxicity Assessment              | X  | X  | X  |
| Lab/Diagnostic Tests                    | 3.7              | Immunogenicity/ Pharmacokinetics | X a   |  |  |

Abbreviations: CTCAE = Common Terminology Criteria for Adverse Events; IG = immunogenicity; QD = everyday; PK = pharmacokinetic; SC = subcutaneous.

a Only if a patient experiences a suspected systemic hypersensitivity reaction involving the skin or mucous membranes, respiratory, cardiovascular, gastrointestinal, urinary or other systems, after an administration of study drug(s), after patient’s stabilization, blood samples for IG and PK analysis will be taken at the following time points: as soon as possible after the onset, at the resolution of the suspected hypersensitivity event, at 30 days (±3 days) after the event, and 12-16 weeks after the event.

### **Appendix C – Birth Control Methods that May Be Considered Highly Effective**

Methods that can achieve a failure rate of less than 1% per year when used consistently and correctly are considered as highly effective birth control methods. Such methods include:

- combined (estrogen and progestogen containing) hormonal contraception associated with inhibition of ovulation 1:
  - oral
  - intravaginal
  - transdermal
- progestogen-only hormonal contraception associated with inhibition of ovulation:
  - oral
  - injectable
  - implantable
  - intrauterine device (IUD)
  - intrauterine hormone-releasing system (IUS)
  - bilateral tubal occlusion
  - vasectomized partner
  - sexual abstinence

Guidance on the acceptable contraception methods can be found here:

[http://www.hma.eu/fileadmin/dateien/Human\\_Medicines/01-About\\_HMA/Working\\_Groups/CTFG/2014\\_09\\_HMA\\_CTFG\\_Contraception.pdf](http://www.hma.eu/fileadmin/dateien/Human_Medicines/01-About_HMA/Working_Groups/CTFG/2014_09_HMA_CTFG_Contraception.pdf)

## **Appendix D – RECIST v.1.1 Criteria**

The primary efficacy endpoint is objective response rate. Tumor response will be assessed by RECIST v.1.1 guidelines on images obtained with CT scans. The CT scans will be performed at Baseline during Screening (within 4 weeks prior to Day 1), at Week 8 ( $\pm 7$  days) and every 8 weeks ( $\pm 7$  days) during the study treatment and during the first year from discontinuation of the study treatment, every 12 weeks ( $\pm 7$  days) during the second year, and every 16 weeks ( $\pm 7$  days) thereafter. Tumor assessment will be repeated until disease progression, death, or receipt of new anti-cancer therapy, or until study completion, whichever is first, whether or not study treatment was administered. Radiologic studies for antitumor response will be repeated at the end-of-treatment visit only if required per the defined study imaging schedule.

### **Definition of Measurable and Non-Measurable Lesions**

#### **Measurable Lesions at Baseline**

The definition of a measurable lesion at Baseline is dependent on the technical factors of the imaging studies that were used to evaluate the patient. The recommendations for the imaging parameters are based on the American College of Radiology (ACR) Practice Guidelines and Technical Standards. The ACR Practice Guidelines and Technical Standards define principles and technical parameters of radiologic and radiation oncology practice, which should generally produce desired health care outcomes. They describe a range of acceptable approaches for the diagnosis and/or treatment of disease for most patients, in most circumstances. Given differences in training, experience, and local conditions, the ACR Practice Guidelines and Technical Standards acknowledge the need for health care providers to exercise their independent medical judgment in making decisions regarding the use and specific details of any procedure.

For spiral CT scanning, the recommendation is for a slice thickness of 5 mm or less.

The RECIST v.1.1 guideline recommends spiral CT images for chest, abdomen, and pelvis should be performed using 5 mm reconstructions, but it is not explicitly stated as a requirement (Eisenhauer, Therasse et al. 2009).

In preparing the technical specifications, we have followed the guidelines of the ACR, as 5 mm reconstructions are not the standard in the US or the rest of the world. Our proposal for modifying the size of measurable lesions at Baseline to 2 times the reconstruction interval of the Baseline/Screening studies is consistent with the RECIST definition for a measurable lesion.

- Conventional CT should be performed with contiguous cuts of 10 mm or less in reconstruction interval. Spiral CT should be performed by use of a 5–8 mm contiguous reconstruction interval or less, whereas the neck and brain CTs should be done at 5 mm or less.
- Lesions that can be accurately measured in at least 1 dimension with the longest diameter (LD)  $\geq 20$  mm with conventional techniques when the conventional scans are performed with a reconstruction interval of 10 mm or less are measurable lesions.

- Lesions that can be accurately measured in at least 1 dimension with the LD being 2 times the reconstruction interval (RI) of the spiral CT scan. Depending on the RI of the spiral CT (5–8 mm or less recommended) measurable lesion size may be  $\geq 10$ –16 mm. For example, a spiral CT scan done at 8 mm RI would have a minimum lesion size of 16 mm in the longest dimension. The minimum size of a measurable lesion is 10 mm.
- Although initially identified as measurable lesion  $\geq 10$  mm, target lesions may in time reduce to  $< 5$  mm in their LD. In those circumstances in which the target lesion LD is less than the 5-mm minimum for measurability, the lesion LD should be recorded as 5 mm.
- In the instance in which the reconstruction interval has changed from the Baseline to subsequent time points, it would be at the discretion of the radiologist whether this would affect interpretation. A note is made in the comment section of the source document, if applicable. The definition for target disease would not change and would be determined on the basis of the Baseline scan.

### **Non-Measurable Lesions**

All other lesions that do not meet the criteria for measurable disease as well as other truly non-measurable lesions (eg, ascites, bone lesions, pleural effusion, etc.) are considered non-measurable.

### **Definition of Target, Non-Target, and New Lesions (RECIST v1.1 Guidelines)**

#### Target Lesions

Up to 5 target lesions, a maximum of 2 per organ, will be chosen for measurement over the course of the study. The distribution of these target lesions should be representative of the patient's overall disease. Target lesions should not be chosen from a previously irradiated area unless lesions in those areas have documented progression.

Target lesions must be measurable at Baseline. These lesions will generally be the largest lesions, most reliably measured, and most representative of the patient's sites of disease.

For any target lesion at any time point, measurements will be taken and recorded unidimensionally. The longest dimension of each target lesion will be measured and recorded. The longest dimension of the target lesions will be summed to obtain the Sum of the Longest Diameters (SLD). The Baseline SLD will be used as reference to further characterize the objective tumor response of the target lesions. For the consideration of progressive disease, the nadir of the SLD for the target lesions will be used as reference.

For cases where there is no target lesion identified, tumor assessment for progression should be done based on non-target lesion assessments or the development of new lesions.

Response (PR or CR) and SD will not be assessed in patients for whom target lesions are not identified at Baseline. The following conventions will be applied in selecting target lesions in patients who have received prior radiation therapy:

- Intrathoracic measurable lesions in the periphery of the lung, just deep to the radiated chest wall concordant with the radiation portal cannot be selected as target lesions. However, if the lesions are more centrally located in the chest and do not appear in regions showing evidence of radiation injury (eg, scarring, radiation pneumonitis, etc.),

they can be selected as target lesions. The assigned radiologist will document descriptions of radiation damage in the comments field.

- Prior bone radiation (eg, vertebral, rib, pelvis, femur, etc., as stated on the Prior Radiation Therapy Form would not preclude the selection of measurable lesions in adjacent structures unless signs of radiation injury are evident (eg, scarring).
- Prior soft tissue radiation (eg, supraclavicular radiation, radiation of internal mammary lymph nodes, etc. as recorded on the Prior Radiation Therapy Form would preclude the selection of measurable disease in the site of radiation unless the site confirms on the Prior Radiation Therapy Form that the lesions are new since radiation was completed.

### Non-Target Lesions

All of the sites of disease present at Baseline not classified as target lesions will be classified as non-target lesions. Non-target lesions must be qualitatively assessed at each subsequent time point. Examples of non-target lesions include:

- All bone lesions, irrespective of the modality used to assess them;
- Leptomeningeal disease;
- Lymphangitis of the skin or lung;
- Cystic lesions;
- Irradiated lesions that have not shown progression;
- Measurable lesions beyond the maximum number of 10;
- Groups of lesions that are small and numerous; and
- Pleural effusion/pericardial effusion/ascites.

### New Lesions

Unequivocal new lesions are those that were not present at Baseline. At each time point, the presence of new lesions will be determined. New multi-focal or miliary disease of any size is considered a new lesion.

Lesions that are encountered (subsequent to the Baseline) in anatomic locations that were not scanned at Baseline will be considered new lesions and will represent progressive disease.

Lesions that were present which subsequently resolved and then recurred will be considered new lesions and will represent progressive disease.

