### **Target Lesion Response (RECIST v1.1 Guidelines)**

Percentage change in SLD will be evaluated by the following formulae:

1. When determining CR or partial response:  
 $(\text{Post value} - \text{Baseline value}) / \text{Baseline value} \times 100$
1. When determining progressive disease:  
 $(\text{Post value} - \text{Nadir value since treatment started}) / (\text{Nadir value since treatment started}) \times 100$

The following definitions will be used to evaluate response based on target lesions at each time point after Baseline:

**Complete Response:** Disappearance of all target lesions.

**Partial Response:** At least a 30% decrease in the SLD of target lesions, taking as reference the Baseline SLD.

**Stable Disease:** Neither sufficient shrinkage of target lesions to qualify for PR, nor sufficient increase to qualify for PD, taking as reference the nadir SLD since the treatment started.

**Progressive Disease:** At least a 20% increase in the SLD of target lesions, taking as reference the nadir SLD recorded since the treatment started, or, the presence of one or more new lesions. In addition to the relative increase of 20%, the sum must also demonstrate an absolute increase of at least 5 mm. The appearance of one or more new lesions is also considered progression. The PET scans will not be used to determine target lesion progression or as a criterion for patient withdrawal from the study. Only CT scans or MRIs will be used for those purposes.

**Not Evaluable (NE):** A target lesion present at Baseline which was not measured, or which was unable to be evaluated leading to an inability to determine the status of that particular tumor for the time point in question. If the SLD cannot be determined at a time point and the rules for PD do not apply, a response of CR, PR, or SD cannot be assigned for that time point, and the time point response will be NE.

**Not Applicable (NA):** No target lesions were identified at Baseline. Patients with no target lesions identified at Baseline cannot be assessed for response. These patients will be assessed for progression only.

**Not Done (ND):** Scans were not performed at this time point to evaluate the target lesions.

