**Response Determination (RECIST v1.1 Guidelines)**

Response at each time point will be assessed as a combination of the target and non-target responses as well as the presence of new lesions according to the table below:

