**Best Overall Response – Confirmation of CR and PR**

| Best Overall Response when Confirmation of CR and PR Required |  |   |
|---|--|---|
| Overall Response First Time Point                             | Overall Response Subsequent Time Point | Best Overall Response   |
| CR  | CR                                     | CR  |
| CR  | PR                                     | SD, PD or PR*   |
| CR  | SD                                     | SD provided minimum criteria for SD duration met, otherwise, PD |
| CR  | PD                                     | SD provided minimum criteria for SD duration met, otherwise, PD |
| CR  | NE                                     | SD provided minimum criteria for SD duration met, otherwise, NE |
| PR  | CR                                     | PR  |
| PR  | PR                                     | PR  |
| PR  | SD                                     | SD  |
| PR  | PD                                     | SD provided minimum criteria for SD duration met, otherwise, PD |
| PR  | NE                                     | SD provided minimum criteria for SD duration met, otherwise, NE |
| NE  | NE                                     | NE  |

Abbreviations: CR = complete response; NE = not evaluable; PD = progressive disease; PR = partial response; SD = stable disease.

\*If a CR is truly met at first time point, then any disease seen at a subsequent time point, even disease meeting PR criteria relative to baseline, makes the disease PD at that time point (since disease must have reappeared after CR). Best response would depend on whether minimum duration for SD was met. However, sometimes 'CR' may be claimed when subsequent scans suggest small lesions were likely still present and in fact the patient had PR, not CR at the first time point. Under these circumstances, the original CR should be changed to PR and the best response is PR.

Source: Eisenhauer, Therasse et al. 2009.

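### Appendix D makes any lesion that resolves and is seen again a new lesion and PD, so a patient still in PR by tumor sum becomes a PFS event and duration of response ends

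*Protocol*

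**What the plan says.** Protocol Appendix D, New Lesions, opens with a definition: "Unequivocal new lesions are those that were not present at Baseline". Two special cases follow. One covers lesions in anatomy not scanned at baseline. The other is the sentence at issue: "Lesions that were present which subsequently resolved and then recurred will be considered new lesions and will represent progressive disease". It applies to target and non-target lesions alike, at any size, whatever the patient's response status.

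Three other parts of Appendix D bear on the same event:

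- **Target Lesion Response.** PD by target sum needs 20% growth over nadir, and "In addition to the relative increase of 20%, the sum must also demonstrate an absolute increase of at least 5 mm". New lesions are a separate route: "The appearance of one or more new lesions is also considered progression". PR is "At least a 30% decrease in the SLD of target lesions, taking as reference the Baseline SLD".
- **Response Determination.** Overall response combines target and non-target findings "as well as the presence of new lesions according to the table below". In that table any new lesion gives PD whatever the other two columns show.
- **Best Overall Response, footnote.** The condition for calling reappearing disease PD begins "If a CR is truly met at first time point, then any disease seen at a subsequent time point". The footnote also allows a claimed CR to be changed to PR where "subsequent scans suggest small lesions were likely still present and in fact the patient had PR, not CR at the first time point".

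The endpoints then use the PD call as follows:

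- SAP Table JZGD.6.1, rule 5, makes progression per scan a PFS event.
- SAP 6.5.3.4 ends duration of response at first documented progression.
- Protocol 10.2.1 defines ORR on confirmed responses.
- SAP 6.5.2.1 counts any CR or PR recorded before documented progression, without confirmation. Confirmed ORR is the additional analysis ORR3 in SAP 6.5.2.2.

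**The concern.** A baseline lesion that can no longer be seen and is later seen again was, by the section's own definition, not new. The sentence nevertheless labels it new, and the response table turns that label into PD regardless of total tumor burden. The footnote deals with the same event more leniently: it speaks of reappearance after a true CR, and lets a doubtful CR be revised to PR. A patient in PR or SD, whose disease was never said to be gone, gets no such correction.

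The primary PFS analysis and duration of response are at stake, and ORR in the circumstances set out below. A second problem is consistency. Response is assessed by investigators. A site applying the New Lesions sentence and a site applying the definition, the nadir rule and the footnote can classify identical scans differently.

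**Working it through.** **Sample-size basis.** The plan gives no figure for this rule. Its only related figures are the 90% intervals for 25 patients per arm (Protocol 10.3, SAP 5.2). The exact Clopper-Pearson method reproduces them: 3/25 gives 3.4% to 28.2%, 6/25 gives 11.0% to 42.0%, and 8/25 gives 17.0% to 50.4%. They do not bear on the rule, but they fix n = 25.

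**Formulas (Appendix D, Target Lesion Response).** Change from baseline = (now − baseline)/baseline. Change from nadir = (now − nadir)/nadir. PD by sum needs at least +20% and at least +5 mm over nadir. PR needs at least −30% from baseline.

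**Illustrative lesion sizes (assumed, in mm).**

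| Case | Baseline | Earlier scan | Current scan | vs baseline | vs nadir | By sum | New Lesions sentence |
|---|---|---|---|---|---|---|---|
| A: target reappears at 5 mm | 45+25+10 = 80 | 26+14+0 = 40 (−50%, PR) | 26+14+5 = 45 | −43.75% | +12.5%, +5 mm | PR | PD |
| B: non-target reappears, targets unchanged | 100 | 30 (−70%, PR) | 30 | −70% | 0% | PR, not PD | PD |
| C: target reappears at 10 mm | 60+40 = 100 | 30+0 = 30 (−70%, PR) | 30+10 = 40 | −60% | +33.3%, +10 mm | PD | PD |
| D: reappears before any PR is recorded | 60+20 = 80 | 58+0 = 58 (−27.5%, SD) | 48+5 = 53 | −33.75% | −8.6%, −5 mm | PR | PD |

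If the other target lesions are unchanged, a 5 mm reappearance stays under the 20% threshold whenever the nadir sum exceeds 5/0.20 = 25 mm. In case B a non-target lesion would otherwise be judged by the unequivocal-progression criterion. In case C the two rules agree. In case D the target sum has fallen, yet the visit is PD.

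**Sensitivity to reading.** Appendix D, Measurable Lesions at Baseline, records a target lesion that has shrunk below 5 mm as 5 mm. If the small lesion in case A is read at week 8 as tiny but present, the sum is 26+14+5 = 45 (−43.75%), and the same sum on the repeat scan is a confirmed PR. If it is read as absent, the sums are 40 then 45, and the New Lesions sentence gives PD. The anatomy could be the same in both readings.

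**Effect on each endpoint, case A, reappearance on the confirmatory scan.**

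- *Primary PFS:* event at that scan (Table JZGD.6.1, rule 5), unless an earlier censoring rule applies.
- *Duration of response, SAP 6.5.3.4:* ends at that scan. Protocol 10.5.3.2 requires a confirmed response, so there the patient does not enter the analysis.
- *Confirmed ORR (Protocol 10.2.1, SAP ORR3):* lost. PR followed by PD becomes SD or PD in the best-response table.
- *SAP primary ORR (6.5.2.1):* kept, because the week 8 PR was recorded before progression.

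In case D no PR is recorded before the PD call, so the patient is lost from every ORR that stops at that call. If the PR was already confirmed before the reappearance, no ORR changes, but PFS and duration of response do.

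**Size per patient.** One patient is 1/25 = 4 points of an arm's confirmed ORR. For example, 8/25 = 32% (95% exact CI 14.9% to 53.5%) becomes 7/25 = 28% (12.1% to 49.4%).

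**The case against.** Several points on the other side stand.

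- **The nadir rule is bypassed, not contradicted.** A reader might infer that the sentence contradicts the 20%/5 mm threshold. Appendix D lists new lesions as a separate route to PD, so every new lesion avoids that threshold by design. The conflict lies in calling a baseline lesion new.
- **The definition can be read as a general rule with special cases.** That makes the sentence deliberate rather than accidental. It does not explain why a PR or SD patient is treated more strictly than a patient with a claimed CR. The footnote also never says in terms that reappearance is PD only after CR; that limit is inferred from its condition.
- **A reader might infer that the patient loses the response in the primary analysis.** The SAP primary ORR does not support that once a PR has been recorded.
- **The scenario is narrower than it looks.** The 5 mm recording convention keeps a tiny visible target lesion in the sum, so the sentence bites only when a lesion is declared gone. A 10 mm baseline target is measurable only at reconstruction intervals of 5 mm or less, so the coarser intervals Appendix D allows do not help case A.
- **There is some mitigation.** Suspected pseudoprogression leads to a rescan, and Protocol 10.2.1 bases response on the later scan. SAP ORR4 and PFS Sensitivity Analysis 2 address the same issue. These cover only patients handled as suspected pseudoprogression, and they leave primary PFS and duration of response unchanged.

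**Conclusion.** The concern holds for primary PFS and duration of response: a patient well inside PR by tumor sum becomes a progression event. For ORR it holds conditionally. The confirmed ORR is affected when the reappearance precedes confirmation, and any ORR when it precedes the first recorded PR.

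The size is 4 points of confirmed ORR per affected patient at 25 per arm. The documents give no reappearance rate, so the number of patients cannot be derived; it may be small. A reader might also infer that the rule removes more responses from the arm with more shrinkage and so draws the two ORRs together. Nothing in the documents supports that direction or allows it to be quantified.

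The worked cases rest on assumed lesion sizes. The conflict itself rests only on Appendix D's own text. It should be settled before the ORR data lock, because the remedy is cheap and the ambiguity reaches the trial's main time-to-event endpoint derivation.

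**What to change.** Reconcile the New Lesions sentence with the definition above it, the target-lesion criteria and the best-response footnote. For deriving ORR, PFS and duration of response, state in the SAP before the ORR data lock:

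- A lesion present at baseline that becomes undetectable and is seen again, outside an overall CR, is not a new lesion.
- If it is a target lesion, its diameter returns to the sum and the 20%/5 mm rule over nadir applies.
- If it is a non-target lesion, the unequivocal-progression criterion applies.
- Reappearance after an overall CR follows the existing footnote, including correction of a claimed CR to PR.

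The cost is one sentence in Appendix D, a matching derivation rule in the SAP and a note to sites. Target-lesion visits can be re-derived from recorded diameters. Non-target lesions are assessed qualitatively, so affected visits would need a second look at the archived scans. Some progression dates will move later. Where scanning stopped or an Arm 2 patient crossed over after the PD call, the later date may not be observable and the patient may be censored.

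The PD call also governs treatment discontinuation and crossover. This point proposes no rule for those; the sponsor must reconcile the passages for trial conduct.
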